## Interventions.

Nicotine patch. All participants will receive usual psychiatric care plus an offer of the nicotine patch (up to 8 weeks), dosed per package instructions. At the second pre-quit session, participants will be instructed on patch use. The first 4 weeks of patch will be distributed at enrollment and the second 4 weeks will be distributed at the follow-up visit.

Enhanced Usual Care (EUC). Participants in the EUC condition will receive one in-person counseling sessions during the PHP and a second telephone session the week following: the first session will occur prior to the quit day and will focus on establishing a quit plan and instructing the participant on the use of the nicotine patch; the second session will occur prior to quit day and will assess for any difficulties using the nicotine patch. After the second session, participants will be electronically referred to the RI state quitline. This quitline offers an enrollment call and 5 proactive counseling telephone counseling telephone calls to those who enroll. Quitline staff make up to 3 attempts per call to reach users. Total scheduled counseling time offered is 120 minutes. If the participant is unexpectedly discharged before their first counseling visit, the counselor will choose one of the following options in order of preference ((1) complete the second counseling session early but not on the same day as the first counseling session,(2) have the patient return to the partial hospital program location for the first counseling session, (3) complete the counseling session by phone and mail materials distributed during the counseling session).

ACT Care (AC). Participants in the AC condition will receive one in-person and 6 telephone contacts delivered from an ACT framework. Sessions will last approximately 30 minutes. If the participant is unexpectedly discharged before their first counseling visit, the counselor will choose one of the following options in order of preference ((1) have the patient return to the partial hospital program location for the counseling session, (2) complete the counseling session by phone and mail materials distributed during the counseling session). This intervention is an adaptation of the in-person and telephone protocols developed by consultant [name] to deliver an ACT-based smoking cessation treatment to patients with bipolar disorder. This treatment was found to be feasible to deliver both in person (80% retention, 40% verified abstinent at end of treatment, 90% satisfied with treatment) and by telephone (67% retention, 33% verified abstinence, 100% satisfied with treatment).

The intervention targets the six core processes in ACT: acceptance, cognitive defusion, awareness of the present moment, self as context, defining values, and committed action towards values. In ACT, acceptance means increasing willingness to fully engage in all aspects of experience, as opposed to avoiding unpleasant experiences. Cognitive defusion refers to the separation of oneself from the content of one's thoughts, recognizing that cognition does not necessarily have to drive behavior (i.e., a patient can notice themselves having a thought and choose not to act on it).

Awareness of the present moment means being fully in contact with the present moment rather than dwelling psychologically in the past or the future (e.g., rumination about past failures or worry about future challenges). Self as context refers to the awareness that there is a self, independent of the content of thoughts or experiences that acts as an observer of these events.

Defining values is the process of identifying what is meaningful to individuals. Finally, committed action means making concrete value driven behavior change (as opposed to behavior driven by avoidance). The intervention relies heavily on experiential in-session exercises and metaphors as a means of helping smokers learn *in vivo* to apply ACT principles to the task of quitting smoking.

Counselor training. Counselors with previous experience in ACT will be trained by consultant [name] in the delivery of her ACT for smoking cessation protocol. [name] will review mock sessions of the counselors delivering the treatment and offer feedback to ensure that the counselors are trained to criterion. Counseling

**Table 2: Measures**

Construct	Measure	Enrollment	EOT
Feasibility	% smokers recruited	X	
	% participants completed follow-up		X
Acceptability	% counseling calls completed		X
Safety	CSQ		X
	Rehospitalization		X
Efficacy	K6	X	X
	Abstinence		X
	Cigarettes per day	X	X
	Quit attempts		X
Treatment Targets	AIS	X	X
	CTQ	X	X
Covariates	Demographics	X	
	Tobacco History	X	
	FTCD (Modified)	X	
	MSW	X	X
	Cessation treatment utilization		X

sessions will be audiorecorded and we will rate 10% of sessions for fidelity using a fidelity checklist. Quitline counselors are trained Tobacco Treatment Specialists.

Hennepin Healthcare Research Institute. [name]., is the MPI of the study. She will continue to be involved in the study at her new institution, Hennepin Healthcare Research Institute (HHRI). Her roles will include designing study manuals, protocols and assessments, supervising study counselors, listening to audiorecordings of counseling sessions and providing feedback to study counselors and monitoring study progress.

#### Measures.

Feasibility, acceptability and safety. Feasibility of recruitment and retention will be measured by the proportion of smokers seen in the program during the enrollment period who enroll during the recruitment period. The two existing studies of smoking cessation treatment provided in inpatient psychiatric hospitals reported 69-79% recruitment rate (of those meeting inclusion criteria) and 80% retention. Results in this range will be considered feasible. Feasibility of treatment delivery will be assessed by the number of completed visits in the ACT group. Previous studies of ACT for tobacco cessation have found approximately 65-67% of calls were completed. Results in this range will be considered feasible. Acceptability will be measured at end of treatment using the 8-item Client Satisfaction Questionnaire (CSQ), a reliable and valid questionnaire developed to test health program acceptability. Safety. We will collect information on patient re-hospitalization via chart review and using questions from the 2016 National Health Interview Survey about visits to the emergency room and to the hospital. In addition, we will assess for symptom exacerbation. In addition, we will measure global distress using the K6 scale, a measure of non-specific psychiatric distress that has been used in population samples to discriminate between samples with and without mental illness.

Efficacy. Efficacy will be measured by 7-day point-prevalence tobacco abstinence at end of treatment, verified by an expired breath CO rating  $\leq 6\text{ppm}$ . Finally, we will assess number of serious quit attempts ( $>24$  hours of intentional abstinence).

ACT treatment targets. ACT treatment targets will be measured at both in person visits and during the follow-up call. The two overarching constructs of ACT, acceptance, and commitment will be assessed. Acceptance, will be measured using the Avoidance Inflexibility Scale (AIS), a 13 item, Likert scale, assessing participants' responses to their internal stimuli, including smoking-related thoughts, feelings and physiological sensations. Acceptance has been shown to account for the bulk of the treatment effect of ACT for tobacco cessation in previous studies. Commitment will be measured using the 8-item, Commitment to quitting scale (CTQ).

Covariates. Demographics. We will collect patient demographics (e.g., psychiatric diagnoses, age, race/ethnicity, and age) upon enrollment. Tobacco use history (e.g., number of cigarettes per day, number of years smoking) will be measured at enrollment. Nicotine dependence will be measured at enrollment via the first item of the Fagerström Test for Cigarette Dependence (FTCD). Cigarette withdrawal will be measured at each of the in-person visits and at end of treatment using the Minnesota Nicotine Withdrawal Scale (MNWS), a 9-item self-report measure of DSM withdrawal symptoms. Nicotine patch use will be assessed at end of treatment. We will also assess use of other cessation medications (e.g., prn nicotine replacement, bupropion, varenicline) as well as use of tobacco cessation counseling (quitline, group, individual) during the trial.

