Partial hospitalization is an excellent and underused opportunity to engage patients in tobacco treatment. Inpatient hospital systems provide a good setting to initiate intervention with tobacco use because, unlike private practice, they provide a closed system of providers who see large numbers of patients. By training a few clinicians to intervene and having a system for follow-up, tobacco treatment initiated in this setting could reach a large number of patients. Individuals hospitalized in a psychiatric hospital report high levels of motivation to quit. Two clinical trials of a computerized, stage-based, tobacco cessation treatment administered in inpatient psychiatry found that smokers were interested in tobacco treatment (recruitment rates 69-79%) and that those in the intervention group were more likely to be abstinent following hospitalization than usual care. Post-discharge abstinence rates were low, but increased over time. No safety concerns were found.

Partial hospital programs provide intensive day treatment for individuals in acute psychiatric distress. PHPs are prevalent; in 2010, there were over 400 programs nationwide. Partial hospitals may be an even better place to intervene with tobacco use than inpatient units because: (1) like inpatient psychiatry, there is a closed system of providers who can be trained; (2) patients are accessible; (3) patients are more stable in their illness than inpatients and therefore may be more able to accept and benefit from smoking cessation interventions; (4) partial hospital programs provide a context that allows for goal setting and restructuring of patients' home environments; (5) patients spend the day on a smoke free campus which may reduce opportunities to smoke and provide practice managing cravings; (6) patients go home at night and are encouraged to practice skills that they have learned in their home environment.

Acceptance and Commitment Therapy (ACT) is a promising treatment strategy for smokers living with SMI. ACT is a third wave cognitive behavioral therapy with two key components: (1) acceptance of unpleasant thoughts, feelings or sensations, and (2) commitment to values-guided action despite discomfort. ACT is a general psychotherapeutic approach that has been used successfully to treat a variety of mental health diagnoses including anxiety, depression, and psychosis.

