Several pilot studies show promise for ACT as a treatment for tobacco dependence, including one showing favorable results compared to traditional cognitive behavioral approaches. To date, no large scale (fully powered) trials have been completed on the use of ACT for tobacco cessation.

Most of the ACT for smoking cessation studies have included only non-psychiatric populations. ACT may be particularly well-suited for tobacco cessation in patients with psychiatric comorbidities as: (1) ACT treatments can also be applied to treat mental health symptoms allowing for a consistent treatment framework across diagnosis, (2) the hypothesized mechanism of change (i.e., willingness to experience distress and discomfort in order to live a valued life) may be particularly relevant for smokers with psychiatric comorbidities, who are more dependent and have more severe withdrawal symptoms (i.e., they will experience more

discomfort than average when quitting). There have been two, small, uncontrolled, feasibility studies of ACT for smoking cessation in patients with mental illness. These studies found ACT for tobacco cessation to be feasible in smokers with bipolar disorder and posttraumatic stress disorder. There have been no controlled trials of ACT for smoking cessation in patients with psychiatric comorbidities. More work is needed to assess the feasibility of applying the ACT treatment approach to tobacco cessation treatment with smokers with SMI, particularly among those in acute psychiatric episodes.

**SUBJECT RECRUITMENT:** Source. Participants will be recruited from the Rhode Island Hospital (RIH), Psychiatric Partial Hospitalization program (PHP; See letter from [name], Medical Director of the program). This day treatment program (8AM-2PM) employs the principles of ACT via four group sessions, and individual meetings with both a psychologist and a psychiatrist.

Sample size. We propose a sample size of 20 smokers per group because the primary aim of the R03 grant mechanism is to assess initial feasibility. We will oversample men such that 50% of the sample is male. Based on the current census of the PHP, we anticipate 240 smokers will be seen over the 8-month recruitment period, making it feasible to recruit 40 smokers.

Inclusion criteria. Participants will be male and female, current daily smokers,  $\geq$  age 18, have regular telephone access, and are able to read and write English.

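### Recruitment feasibility is measured over all smokers seen but judged against a 69-79% range for eligible smokers, so recruiting to plan over 8 months (40/240 = 16.7%) falls outside that range

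*Protocol*

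**What the plan says.** The protocol's Measures section, under feasibility, acceptability and safety, takes as its recruitment measure "the proportion of smokers seen in the program during the enrollment period who enroll during the recruitment period". The next sentence reports that two inpatient studies had a "69-79% recruitment rate (of those meeting inclusion criteria) and 80% retention", and the one after it adds: "Results in this range will be considered feasible". Table 2 lists the percentage of smokers recruited without defining a denominator.

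Under Subject Recruitment, the sample size of 20 per group is justified because "the primary aim of the R03 grant mechanism is to assess initial feasibility". The same paragraph says "we anticipate 240 smokers will be seen over the 8-month recruitment period, making it feasible to recruit 40 smokers".

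Eligibility is narrower than being a smoker in the program. Participants must smoke daily, be adults, and "have regular telephone access, and are able to read and write English"; current cessation treatment is an exclusion, apart from bupropion given for a psychiatric indication.

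SAP Aim 1 describes the number recruited against the number of smokers seen in the program during enrolment. It repeats no range, and the SAP states that its analyses are descriptive.

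**The concern.** The measure and its benchmark have different denominators: every smoker seen in one case, eligible smokers in the other. Ineligible smokers and smokers never invited lower the trial's rate but cannot lower the benchmark's. A gap between the two therefore says little about how willing eligible smokers were to take part.

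This bears on the question the trial was sized to answer. Followed literally, a trial that enrolled all 40 participants on schedule would report a recruitment rate far outside the only recruitment range its protocol calls feasible. A reader could take that as poor uptake when it mostly reflects the enrolment target and the choice of denominator.

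**Working it through.** **Inputs.** From the protocol's sample-size paragraph: 20 per group in 2 groups, 240 smokers expected, 8 months. From Measures: the range 69-79%.

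**Planned total.** 20 × 2 = 40, which matches the stated target. The documents give no recruitment percentage; the rates below are derived.

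**Rate if recruitment goes to plan, enrolment open 8 months.** 40/240 = 16.7%. Shortfall from the lower limit: 69 − 16.7 = 52.3 points.

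**Enrolments needed on the stated denominator.** 0.69 × 240 = 165.6 and 0.79 × 240 = 189.6, so 166 to 189 whole participants, more than four times the target (166/40 = 4.15).

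**If enrolment closes on reaching 40.** Smokers arrive at 240/8 = 30 a month.

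| Enrolment closes at | Smokers seen | Rate |
|---|---|---|
| 8 months | 240 | 16.7% |
| 6 months | 180 | 22.2% |
| 4 months | 120 | 33.3% |
| 1.9 months | 57 | 70.2% |
| 1.7 months | 51 | 78.4% |

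The neighbouring values fall outside the range: 40/58 = 68.97% and 40/50 = 80.0%. The all-smokers rate is thus in range only if the trial fills within about the first 2 of its 8 months.

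**Does an eligible denominator solve it?** Not by itself. With 40 enrolled, the rate reaches 69% only if the denominator is at most 57, and 57/240 = 23.75% of smokers seen. The documents give no eligible fraction, so these are assumed values over the full 240:

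| Assumed eligible | Denominator | Rate |
|---|---|---|
| 100% | 240 | 16.7% |
| 80% | 192 | 20.8% |
| 50% | 120 | 33.3% |
| 30% | 72 | 55.6% |
| 25% | 60 | 66.7% |

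The denominator must therefore also be confined to smokers invited while enrolment is open.

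**Who is counted as eligible.** The protocol's Recruitment and Informed Consent section screens for eligibility only after a smoker shows interest. A rate among screened smokers alone would omit those who decline earlier, and the Background cites the same 69-79% as a sign of interest in treatment. Illustration with assumed counts: 40 enrolled, 50 screened and eligible, 20 declining before screening. Without the early decliners the rate is 40/50 = 80.0%; with all of them it is 40/70 = 57.1%. The two fall on opposite sides of 69%, so one rate alone could mislead.

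**The case against.** The best defence is that little depends on this range. The SAP, which is later than the protocol, is descriptive and has no threshold; no go/no-go decision is attached; and Measures openly labels the benchmark as a rate among eligible smokers. All of this stands, and it limits the harm to interpretation. It does not remove the mismatch: the protocol still ties the range to the all-smokers rate, and the SAP keeps that denominator.

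Four stronger readings are tempting, and the documents do not support them.

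- *The trial must fail its own criterion.* The protocol says that results within the range count as feasible. It gives no rule for lower results.
- *The plan assumes 16.7% uptake.* The figure of 240 is offered to show that there are enough smokers to reach 40. The 16.7% is derived, and holds only if enrolment runs the full 8 months.
- *No other feasible range exists.* Measures uses the same sentence for 65-67% of calls completed. The 69-79% range is the only one for recruitment.
- *The male quota distorts the rate by a known amount.* The protocol says "We will oversample men such that 50% of the sample is male" but not how, and gives neither the share of men among smokers nor their uptake.

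A further objection concerns any single replacement rate. The documents do not say how the cited studies handled refusals or when they screened, so it cannot be shown that early decliners belong in the comparison, or that they do not. Nor is the eligibility of early decliners wholly unknown. Recruitment and Informed Consent says that those told about the study already appear to meet the criteria, whereas Procedures has all current daily smokers told at admission. This objection stands, and it is why the fix uses two bounds.

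**Conclusion.** The recruitment criterion is wrong as written and should be corrected, because it concerns the trial's primary aim and the correction is cheap. The denominator mismatch is plain in the text and needs no assumption. The 52-point gap rests on 240 smokers, 40 enrolled and 8 months of open enrolment; closing early narrows it, but the rate reaches the range only if all 40 enrol from the first 51 to 57 smokers seen. No test or treatment comparison is affected.

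A reader might infer that changing the denominator would bring a trial recruited to plan into range. It need not: if more than 57 eligible smokers are invited and 40 enrol, the rate is below 69%. That would then be a finding about uptake, not a product of the denominator.

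**What to change.** Amend the feasibility paragraph of Measures and SAP Aim 1 as follows.

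1. Report enrolled / all smokers seen as reach, with no threshold.
2. Compare with 69-79% only an eligible-smoker rate among those invited while enrolment is open, shown as a pair:
   - upper bound: enrolled / screened and eligible;
   - lower bound: enrolled / (screened and eligible, plus apparently eligible smokers who decline before screening).
3. State that the comparison is inconclusive if the bounds fall on either side of 69%, and that a rate above 79% also counts as feasible.
4. State that with 40 enrolled a rate reaches 69% only if its denominator is at most 57, so smokers seen after enrolment closes, or never invited, must not be counted in the compared rate.
5. Keep a log of smokers seen, invited, declining before screening, found ineligible, not offered a place, and enrolled. Reconcile Procedures with Recruitment and Informed Consent on who is told about the study.

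The cost is wording and a short log; smoking status at admission and eligibility screening are already planned. One limitation remains: the eligibility of early decliners is only apparent, so the lower bound depends on that judgement.

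A minor related change: Measures assesses ACT delivery by completed visits but uses a 65-67% benchmark for calls. Compare the Table 2 measure of counseling calls completed with it instead. First reconcile Procedures (two pre-quit sessions, then up to 5 telephone sessions) with ACT Care (one in-person and 6 telephone contacts). Both total 7 contacts, but they differ on how the second session is delivered and so on the number of calls.

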## PROCEDURES:

Recruitment. Participants will be recruited during PHP treatment. As standard clinical care, all patients are screened for smoking status upon admission. Current daily smokers will be informed about the study at that time and invited to be screened for participation. All women of childbearing potential who would like the nicotine patch will complete a pregnancy test prior to inclusion into the study. Eligible and interested participants will complete an enrollment/pre-quit visit while enrolled in the PHP, which includes a baseline assessment, random assignment to a condition, the first counseling session and 4 weeks of nicotine patches (to be started on the quit day). The enrollment visit can be on the same day as the first pre-quit visit counseling but doesn't need to be. Participants will then complete a second pre-quit counseling session (within one week of the pre-quit session but before discharge). If the participant is to be discharged before their first or second counseling session, the counselor will choose one of the following options in order of preference ((1) complete the second counseling session early but not on the same day as the first counseling session,(2) have the patient return to the partial hospital program location for the first or second counseling session, (3) complete the counseling session by phone and mail materials distributed during the counseling session). Following the second counseling session, participants will continue in their assigned post-discharge intervention consisting of up to 5 Quitline or ACT telephone sessions.

Study outcomes will be assessed at the end of the counseling treatment at an in-person visit 5 weeks after their visit 2 date OR 24 hours after the last counseling session by a research staff member, whichever is later. As an incentive for completion of the follow-up assessment, those in either group who complete this visit will receive \$20 compensation and an additional 4 weeks of the nicotine patch. We will try to schedule visits around existing appointments in the hospital system to increase compliance.

Randomization will use block randomization, unknown to the counselor or the participant. In order to balance any benefit of bupropion treatment in combination with the nicotine patch across treatment conditions, randomization will be stratified by bupropion use.

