Participant payment. Participants will be paid \$20 for the enrollment/pre-quit visit and \$20 for the follow-up assessment visit. If the first counseling session happens by phone, participants will be paid for the assessment with a mailed gift card with a \$20 value, instead of \$20 cash. Participants will be paid \$5 per telephone counseling session completed. Payment for the counseling sessions will be paid at the follow-up visit and is contingent on follow-up visit attendance.

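### Does it matter that ACT session delivery is counted in visits, benchmarked in calls and reported in sessions?

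*Protocol*

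**What the plan says.** The protocol's Measures section sets the delivery criterion in three sentences. The first names the measure, which is a count of visits: "Feasibility of treatment delivery will be assessed by the number of completed visits in the ACT group". The second supplies the benchmark, which is a percentage of calls: "Previous studies of ACT for tobacco cessation have found approximately 65-67% of calls were completed". The third is the rule for judging the outcome: "Results in this range will be considered feasible". Table 2 lists the percentage of "counseling calls completed". The SAP, under Aim 1, promises descriptive statistics on the number of sessions completed in each group and gives no cut-off. It opens by saying that the analyses are descriptive because the samples are small.

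The schedule is described twice. Under Interventions, ACT participants "will receive one in-person and 6 telephone contacts delivered from an ACT framework", which makes seven. Under Procedures, the enrollment visit is one "which includes a baseline assessment, random assignment to a condition, the first counseling session and 4 weeks of nicotine patches"; a second pre-quit session follows, and then "participants will continue in their assigned post-discharge intervention consisting of up to 5 Quitline or ACT telephone sessions". That is two plus up to five, again seven.

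**The concern.** Three words are used for what should be one quantity, and a count is set against a percentage. Nowhere is the denominator stated. Depending on the reading it could be seven contacts, six telephone contacts, or the five telephone sessions after discharge. The first session can also move to the telephone: the Participant payment paragraph provides for this ("If the first counseling session happens by phone"), and no rule says whether it then counts as a call. Read literally, the range has no rule for a result above 67% either.

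This is the only numeric criterion for treatment delivery, in a trial whose stated purpose is initial feasibility. If the unit were chosen after the data were seen, the choice could decide whether delivery is described as feasible.

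**Working it through.** **Inputs.** 20 participants per group (Protocol, Sample size). Seven scheduled ACT contacts, of which six are by telephone (Interventions) or up to five follow the two pre-quit sessions (Procedures). Benchmark of about 65-67% (Measures). The completion rate for the first session is not given; 80% to 100% is assumed. The benchmark is quoted from earlier studies and not derived in the documents, so there is no figure of the plan's own to reproduce.

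**Counts inside 65-67%.**
- All contacts, 20 × 7 = 140: 0.65 × 140 = 91.0 and 0.67 × 140 = 93.8, so 91 to 93.
- Six calls, 20 × 6 = 120: 78.0 to 80.4, so 78 to 80.
- Five calls, 20 × 5 = 100: 65 to 67.

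**Gap between the two main counts.** Let f be the completion rate of the first session and c that of the six calls. The all-contact rate is (f + 6c)/7, so it exceeds the call rate by (f − c)/7.
- Call rate at 65%, f = 1: (1 + 3.90)/7 = 70.0%, a gap of 5.0 points.
- All-contact rate at 65%, so c = (7 × 0.65 − f)/6. With f = 1, c = 3.55/6 = 59.2%, a gap of 5.8 points. With f = 0.8, c = 3.75/6 = 62.5%, a gap of 2.5 points.

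**Where a 65% floor gives different answers.** Let F be the number of first sessions held and K the number of calls completed. All contacts pass if F + K ≥ 91; calls pass if K ≥ 78. The answers differ when K lies between 91 − F and 77:

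| First sessions held | Calls giving different answers |
|---|---|
| 20 of 20 | 71-77 of 120 |
| 18 of 20 | 73-77 |
| 16 of 20 | 75-77 |
| 13 of 20 | none |

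**How often that happens.** Calls were modelled as 20 independent beta-binomial counts of six, with an assumed within-person correlation of 0.3 or 0.5.
- True call rate 65%, F = 20: 28.6% (correlation 0.3) or 25.1% (0.5).
- True call rate 65%, F = 16: 13.7% or 11.7%.
- True call rate 75%, F = 20: 4.6% or 6.6%.

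**The five-call reading.** This widens the gap. If all 20 complete both pre-quit sessions and 59 of the 100 later calls, the rates are 59/100 = 59.0%, (20 + 59)/120 = 65.8% and (40 + 59)/140 = 70.7%.

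**The wording, side by side.** Under Interventions, both the usual-care and the ACT paragraphs deal with discharge before the first counseling visit, and the remedy in each is to hold that counseling session some other way. The two words name the same event. Reading visits as in-person attendance only would leave one ACT visit per participant, which could not sensibly be set against a benchmark for calls. The Measures section and the SAP therefore both point to all counseling contacts, and that total is seven under either description of the schedule. A first session moved to the telephone does not alter a count of seven.

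**The case for a change.** The strongest contrary case is that the criterion should be fixed before the data are seen. Elsewhere the protocol does use visit for in-person attendance, such as the follow-up assessment, so the words are not perfect synonyms. Table 2 plainly says calls. One plausible dataset can fall below, inside or above the range according to the unit. Stating the denominator would cost a line of text and no new data, because sessions are already counted and completed calls are paid for individually.

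Part of this stands. The denominator is unstated, and the comparison with the benchmark may not be like for like. The two sections also differ on whether the second ACT session is by telephone or, where possible, in the program; those passages need reconciling as text, although the total of seven is unaffected.

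The rest is weaker. The mismatch exists only if the benchmark studies left in-person sessions out of their calls, and only their titles are available here. Making calls the governing figure would go against the measure named in both the Measures section and the SAP. The missing rule above 67% depends on reading an approximate reference value as a closed interval; few readers would call 75% completion infeasible. A confidence interval would not settle the matter: at 65%, with six calls each and the same correlations, its half-width is about 14 to 17 points, against a gap of 2.5 to 5.8.

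**Conclusion.** No change to the plan is needed. The loose wording is real, but it leaves out a detail that an analyst would supply in the ordinary course: report completed sessions out of seven, with the telephone calls visible beside them, and read the benchmark as roughly 65% or better. The SAP's session counts are sound as written. No inference, progression or stopping decision in either document hangs on the 65% figure, so a reader given the counts loses nothing.

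Under the six-call schedule the two counts differ by 5.0 to 5.8 points near 65% with every first session held, and by 2.5 points at 80% first-session completion when the all-contact rate is 65%. The description could change only in a band of three to seven calls out of 120. The five-call reading gives a larger gap, 11.7 points in the example, but it requires dropping two sessions from a measure that most naturally includes them.

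This conclusion rests on 20 ACT participants, on first-session completion between 80% and 100%, and on the reading of visit and session as the same thing. It would be weaker if a later document tied a go or no-go decision to the 65% figure; neither document does.
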